## 1 Background

Aggressive behavior can be largely divided into either instrumental aggression, which is purposeful aggression to obtain a desired outcome, or impulsive aggression, which is sudden, inappropriate aggression mounted in the context of strong emotion such as anger or frustration. Impulsive aggression frequently complicates severe neuropsychiatric disorders occurring across the lifespan, worsens outcomes, and isolates patients from their communities. Management of persistent impulsive aggression is an unmet challenge for diverse healthcare settings such as residential and nursing treatment facilities, civil and forensic psychiatric hospitals, and criminal justice settings. For example, while the majority of people with schizophrenia spectrum disorders are not violent, such conditions confer an aggregate increased risk of violence and aggression, with more than half of patients in forensic psychiatric settings diagnosed with schizophrenia. In recent decades, such patients have increasingly been institutionalized in prisons and jails at a cost of more than \$14 billion, yet still receive substandard care and have high rates of reincarceration. Vast expenditures to treat aggression also occur in non-correctional settings. For example, one-third of the total \$236 billion cost to treat Alzheimer's disease in the U.S. is spent to manage behavioral and psychological symptoms, including aggression. Current treatment approaches for aggression in neuropsychiatric disorders incorporate environmental, behavioral, and pharmacological interventions, yet aggressive behaviors commonly remain treatmentresistant. For these patients, psychopharmacological agents with diverse pharmacological actions are trialed off-label, despite limited pathophysiological rationale, inconsistent clinical benefit, and increased morbidity or mortality. To address this growing need with important individual and societal implications, novel therapeutic approaches must be designed based on an increased understanding of the neural circuits governing aggressive behavior.

## 2 Rationale and specific aims

This human laboratory study seeks to test the hypothesis that activation of nicotinic acetylcholine receptors (nAChRs) in the brain will reduce impulsive behavior in response to negative emotional cues as compared to neutral emotional cues. Because impulsive action during negative mood states is strongly correlated with impulsive aggression in both healthy individuals and individuals with schizophrenia (discussed below), our overarching, long-term goal is to determine whether nAChRs in general as well as specific nAChR subclasses might represent novel treatment targets to reduce impulsive aggressive behavior, a significant public health problem.

Nicotinic acetylcholine receptors are a large family of excitatory, pentameric, ionotropic, ligand-gated ion channels located throughout the brain and the remainder of the body. Their endogenous ligand is acetylcholine, yet this family is defined by their common activation by nicotine. Interestingly, anti-aggressive, or "serenic" effects of nicotine have been demonstrated across a number of animal models, including mice, rats, and non-human primates, and multiple human laboratory studies demonstrate an anti-aggressive effect of nicotine in humans. As detailed in section 3.1, our laboratory has also demonstrated that acute administration of nicotine at relatively low doses results in reduction of aggressive behaviors in mouse models. Because nicotine is active at all nAChRs, we explored this mechanism further and found that hippocampal alpha-7 nAChRs were both necessary and sufficient for nicotine's serenic effect. Consistent with these findings, there is substantial evidence in humans that reduction of alpha-7 nAChR signaling enhances aggressive behavior, including in individuals with 15q13.3

microdeletion syndrome, a genetic disorder resulting from the deletion of the region of chromosome 15 containing the gene coding for alpha-7 nAChRs. We have also translated these findings into human clinical populations. We recently demonstrated the safety and efficacy of transdermal nicotine to reduce aggression and irritability in young adults with autism spectrum disorder, described in section 3.2. This work, along with other previous case studies in humans, supports targeting nAChRs using transdermal nicotine to reduce aggressive behaviors.

While our studies in mice suggest a direct effect of nAChR stimulation on aggression through activation of the alpha-7 nAChR and are supported by our results using transdermal nicotine in humans, to our knowledge no previous studies have directly examined the relationship between pharmacological targeting of nAChRs using transdermal nicotine and effects on impulsivity in the context of emotional cues in humans. We now aim to directly test this hypothesis using an Emotional Go/NoGo task in subjects with schizophrenia and healthy controls to determine whether transdermal nicotine improves impulsive behavior and neural correlates in the context of negative and neutral valence cues. Given the relationship between impulsivity and aggressive behavior, the findings of this proposed study will strongly inform future studies of targeting nAChRs broadly and alpha-7 nAChRs more specifically to identify novel treatments for individuals with severe neuropsychiatric disorders struggling with persistent pathological impulsive aggression.

#### 3 Animal studies and previous human studies

#### 3.1 Animal studies

There exists an extensive literature on the effects of nicotine on animal behavior. As noted above, nicotine has a substantial evidence base suggesting it may have specific serenic effects, i.e. the ability to reduce aggressive behavior (reviewed in 42). Our laboratory has performed several lines of studies aimed at understanding how nAChRs. in particular alpha-7 nAChRs, regulate aggressive and related behaviors in mice. We first replicated previous studies demonstrating a dose-dependent reduction in aggressive behavior by intraperitoneal administration of nicotine. We then found that blockade of alpha-7 nAChRs, but not beta-2-containing nAChRs, blocked the serenic effects of nicotine, implicating a specific role for alpha-7 nAChRs in nicotine's serenic effects. We also found that specific agonism of alpha-7 nAChRs through the alpha-7 nAChR partial agonist GTS-21 recapitulated nicotine's serenic effects. Consistent with alpha-7 nAChRs localization on GABAergic inhibitory interneurons in the dentate gyrus of the hippocampus, we found that GTS-21 reduces activation of the dentate gyrus, and that knockdown of alpha-7 nAChRs reduces GTS-21's serenic effect. These findings suggest that nicotine exerts its effect, at least in part, via hippocampal inhibition thorugh alpha-7 nAChR signaling, consistent with findings from human neuroimaging studies.

Effects of nicotine and nAChR stimulation on impulsivity in rodents have also been studied, in part inspired by the relationship between higher levels of smoking in individuals with neuropsychiatric disorders demonstrating poor impulsive control, such as attention deficit hyperactivity disorder (ADHD) and schizophrenia. Mice performing an operant task that measured premature and signaled nose pokes and performance efficiency found that acute administration of nicotine improved performance efficiency, however chronic nicotine and nicotine withdrawal did not affect performance efficiency. However, interestingly forms of motor of choice impulsivity do not rely on beta-2contaning nAChRs. Mice with genetic deletion of the alpha-7 nAChR demonstrate increased impulsivity compared to wildtype mice in the five-choice serial reaction time task. whereas no other nAChR knockout mouse line demonstrated changes on this task. Interestingly, encenicline (EVP-6124), also an alpha-7 nAchR partial agonist, demonstrated improvements in impulsive action in rats in the 5 choice-continuous performance task. These findings support the relationship between the alpha-7 nAChR and regulation of impulsivity, as well as the potential to improve impulsive responding through its pharmacological targeting by nicotine.

#### 3.2 Human studies

While the effects of nicotine on response inhibition to emotional cues are unknown, previous studies of acutely administered nicotine in humans have shown effects on closely related behavioral constructs and effects on hippocampal inhibition, which we believe is mechanistically important for nicotine's serenic effects. Transdermal nicotine improves performance on the Continuous Performance Test Identical Pairs (CPT-IP) Version in both healthy controls and non-smoking patients with schizophrenia, with improvements to a greater extent in the schizophrenia patients. These findings extend previous work demonstrating positive effects on attention in patients with schizophrenia of acutely administered nicotine. Clinical trials and case series have demonstrated effects of nicotine on reduction of agitation and aggression in subjects with schizophrenia presenting to an emergency department and in elderly subjects with severe dementia. Nicotine was also shown in subjects experiencing nicotine

withdrawal to return provoked aggression in a laboratory paradigm back to baseline levels.

Multiple lines of evidence suggest that pan-activation of nAChRs by nicotine, and more selective activation of alpha-7 nAChRs may influence aggression and related behaviors through effects on regulatory circuitry of affect. For instance, an open label study of transdermal nicotine recently demonstrated substantially improvement in mood symptoms in a population of older adults with late-life depression, in agreement with multiple previous studies reporting improvement in mood symptoms by transdermal nicotine. Our group also found in a secondary analysis of data from a randomized, double blind, placebo controlled study of GTS-21 in patients with schizophrenia that GTS-21 exerts a specific beneficial effect on affect and mood, as measured by the Brief Psychiatric Rating Scale.

Several studies have explored the effects of acute administration of nicotine and selective alpha-7 nAChR agonists on brain activity in regions important for cognition, impulsivity, and aggression. For example, acute administration of transdermal nicotine, 7 mg, in subjects with schizophrenia restored connectivity in the ventral attention network during a go/no-go task with environmental noise distractors, as well as modulated neuronal responses in several brain regions during an auditory selective attention task with environmental noise distractors. An alpha-7 partial agonist was also shown to reduce hippocampal hyperexcitability during a smooth pursuit eye movement task in subjects with schizophrenia, as well as influence default mode network activity in schizophrenia. Positron Emission Tomography (PET) studies also interestingly demonstrated an interaction between trait hostility and brain metabolism in smokers and non-smokers administered acute nicotine by transdermal patch performing a provoked aggression task.

Taken together, previous investigation suggests that acute administration of nicotine in subjects with schizophrenia can influence cognitive processes related to impulsivity and aggression, and target neural substrates overlapping with key brain regions for aggression and impulsivity identified from mouse models. These studies provide strong rationale to directly test the effects of nicotine on response inhibition to emotional cues, which would provide strong evidence to support targeting nAChRs for aggression and related behaviors in clinical populations.

## 4 Inclusion/exclusion criteria

#### 4.1 Inclusion criteria for schizophrenia subjects

- 1. Men and women age 18 65.
- 2. Communicative in English.
- 3. Provide voluntary, written informed consent.
- 4. Physically healthy by medical history, and ECG examination.
- 5. BMI > 17.5 and < 45.
- Diagnosis of schizophrenia (ICD-10 F20) or schizoaffective disorder (ICD-10 F25) confirmed by Structured Clinical Interview for DSM-V (SCID) or diagnostic interview with a trained clinician.
- Stable medication regimen over at least the past two weeks, including the use of either an oral or intramuscular administration of an antipsychotic medication. Additionally, subjects may take any prescribed medication aside from a nicotine-

containing product as long as it has been regularly taken over the past two weeks, including as-needed ("PRN") medication.

- 8. Negative urine toxicology and negative urinary cotinine (to confirm no recent nicotine use) at screening.
- 9. Does not meet criteria for substance or alcohol use disorder per the SCID over the past 6 months
- 10. For females, no longer of child-bearing potential, or agreeing to practice effective contraception during the study (e.g., established use of oral, injected or implanted hormonal methods of contraception; placement of an intrauterine device [IUD] or intrauterine system [IUS]; barrier methods: condom with spermicidal foam/gel/film/cream/suppository or occlusive cap [diaphragm or cervical/vault caps] with spermicidal foam/gel/film/cream/suppository; male partner sterilization; or true abstinence when this is in line with the preferred and usual lifestyle of the subject); and,
- 11. For females of child-bearing potential, must have negative urine pregnancy test at time of screening visit and before each testing day.
- 12. Not breastfeeding/nursing at time of screening or at any time during the study.

#### 4.2 Exclusion criteria for schizophrenia subjects

- 1. Age less than 18 or greater than 65.
- 2. Not communicative in English.
- 3. Unable to provide written informed consent.
- 4. Active suicidal ideation or suicidal behavior.
- 5. Current, unstable medical or neurological illness or significant abnormality on ECG.
- 6. History of severe head trauma.
- 7. BMI < 17.5 or > 45.
- 8. History of allergy to transdermal patches.
- 9. Screening visit resting heart rate > 110 or < 50 beats per minute, or known history of clinically significant cardiac rhythm abnormalities.
- 10. Screening visit systolic blood pressure > 160 or < 90, or diastolic blood pressure > 95 or < 50.
- 11. Positive urine toxicology or positive urine cotinine during screening.
- 12. Meets criteria for diagnosis of substance or alcohol use disorder by SCID within the past 6 months.
- 13. Reports any tobacco smoking or nicotine use over the past month.
- 14. Not taking an antipsychotic medication.
- 15. Positive urine pregnancy test at time of screening, before each testing day, or any potential concern for pregnancy at any time during the study
- 16. Breastfeeding/nursing at time of screening or at any time during the study.

#### 4.3 Inclusion criteria for healthy controls

All of the above except for subjects will be psychiatrically healthy and not taking psychotropic or potentially psychoactive prescription medication.

#### 4.4 Exclusion criteria for healthy controls

All of the above and in addition:

- 1. Current use of psychotropic or potentially psychoactive prescription medication.
- 2. Major psychiatric disorder as determined by DSM-5 (schizophrenia, major depression, bipolar disorder, obsessive-compulsive disorder, post-traumatic stress disorder, etc.)

## 5 Enrollment/randomization

#### 5.1 Subject recruitment and enrollment

The research team will identify potential subjects by morning reports at the Psychotic Disorders Research Program at the Vanderbilt Psychiatric Hospital and other IRB approved screening information, and/or by review of provider's caseloads at Vanderbilt using eStar/EPIC. Potential subjects may also be identified by broadly targeted advertisements with IRB approval. Patient information will be reviewed only for the purposes of determining possible eligibility for the study. All screening information obtained during these reviews will be documented on a screening form or in a passwordprotected database. Screening databases will include inclusion/exclusion information, as well as the patient's name, medical record number, appointment times/dates (for outpatients), and the name of the clinical care provider. All identifying information, such as name, medical record number, and contact information, will be stored in a passwordprotected database. These databases and subject screening forms will be kept for internal monitoring purposes only (i.e., tracking of primary reasons for exclusion from the study). When adult patients (ages 18 to 65) are recruited directly from a mental health clinic or hospital, the subject's clinical care provider will first determine whether or not it is appropriate for us to invite the subject for participation in the study, and the subject must agree to being approached. Adolescent patients (13-17 years old) will not be recruited for this study. Advertising materials may be distributed to physicians' offices and outpatient clinic waiting rooms for the purpose of informing the patient and clinical care providers about the study, but providers who are not part of our study staff will not be asked to describe any part of the study to the patient. Providers will only be asked to inquire about the patient's interest in hearing about research in general. Providers may be contacted by study staff through email, phone, secure EPIC messaging, face-to-face, or by flagging patient charts through front desk staff or inpatient unit staff. Information will not be provided to front desk staff or inpatient unit staff regarding which study the patient is being considered for. We will only recruit patients who are stable. Patients who initiate contact with study personnel in response to an advertisement or flyer will be carefully prescreened and have a thorough clinical evaluation by the study doctor, study coordinator, or study personnel to determine stability of mood and medication. Patient information contained in subject databases may be used to telephone potential subjects. These databases will be comprised of subjects who have given prior consent to be contacted by various researchers about participation in research.

#### 5.2 Process of consent

Consent will be obtained from participants in a private office at the VPH on the screening visit. The subject and one of the investigators will necessarily be present for the consent process. Participants who are accompanied by a family member or caregiver will be allowed the option of having that person in the room if desired. The inclusion and exclusion criteria will ensure that participants have capacity for informed consent (see below). Participants will be given ample time to ask questions during the consent procedure, and to consult family members or caregivers prior to making a decision if they so wish. Participants will be informed during the initial telephonic contact that they will be monetarily compensated for this initial visit whether or not they decide to participate in the study.

## 5.3 Evaluation of subject capacity to provide informed consent

During the screening process, the details of the study will be explained carefully to the subject. After time has been permitted for the participant to ask any clarifying questions, the subject will be asked to summarize their understanding of the procedures, risks and benefits of the study using a "talk back" method. The study personnel will address any inaccuracies, but after two attempts at clarification, if a subject is unable to give a reasonable account of the study procedures, risks and benefits, they will be considered to not have capacity for consent. As a board-certified psychiatrist, [name] has extensive experience in capacity evaluations of individuals with psychiatric disorders, and will ensure research staff is trained to appropriately determine capacity to consent to the research study.

#### 5.4 Randomization

Treatment order will be block randomized by a member of the Center for Cognitive Medicine within the Department of Psychiatry at VUMC who is not otherwise involved in this study. All investigators and subjects will be blinded to treatment order.

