performed in 5 blocks of 32 trials, with 3 emotional blocks with angry/fearful/sad/disgust faces and 2 non-emotional blocks (Figure 1). Each stimulus is presented for 1 s with a 1 s interstimulus interval. In each block the subject is instructed on the go/no-go targets, each comprising 50% of the task stimuli, with instructions changing at the halfway point in each block. Each block contains two instructions. For example: Emotional blocks: go-angry/nogo-fear or go-fear/nogo-angry; Non-emotional blocks: go-male/nogo-female or go-female/nogo-male (Figure 2). Error rates and reaction times are recorded.

Figure 2 Emotional Go/NoGo schematic. Subjects are given a target instruction at the start of each block for 6 seconds. There is 1 second of blank screen between each 1 second stimulus presentation. In this schematic, the subject would press a key ("Go") when presented with the first stimulus (angry; green border represents the correct response is "Go". This border would not be present in the actual task), and withhold pressing a key for the second stimulus (sad; red border).

Subjects will be monitored for at least 30 minutes after patch removal to confirm the absence of side effects that would compromise their safety upon leaving the hospital.

Subjects will return for day 2 of testing not less than 5 days following day 1. On day 2, subjects will receive the treatment they did not receive on day 1. They will be asked a series of standard questions to assess for the presence of any side effects following their initial study day. If female, they will again be administered a urine pregnancy test to confirm the absence of pregnancy. The remainder of the procedure will be identical to day 1.

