## 12 Statistical considerations

#### 12.1 Power analysis

Power analysis for error rates and reaction times is based on effect sizes from previous studies of the Emotional Go/NoGo task in subjects with schizophrenia and our preliminary data from a secondary analysis of a clinical trial of the alpha-7 nicotinic agonist GTS-21. With a sample size of 25 subjects, we will achieve 80% power at  $\Box$ lpha = 0.05 to detect a difference from 35% to 10% in the omission error between two experimental conditions within a subject (expected correlation of 0.60) and to detect an effect size of 0.6 in the mean reaction times between the control and intervention conditions within a person using paired t-test at alpha = 0.05. The dropout rate in a similar published acute crossover study of schizophrenia patients was ~15%. We thus anticipate needing to enroll 30 subjects to result in 25 completers for an appropriately powered study. We will match this group with a healthy control sample of similar size.

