#### 12.2 Data analysis plan

Omission error rate will be analyzed using non-linear mixed effects modeling of a binary outcome omission error (0/1), while reaction time will be analyzed with a linear mixed effects model. In both models, there will be a random effect for subject, a primary fixed independent predictor treatment condition (nicotine or placebo), an independent adjustment variable block valence (emotional vs. non-emotional task), and the interaction of the latter two predictors to examine whether the omission error rate or reaction time between two treatment conditions is moderated by the valence. Significance will be established at alpha = 0.05.

We expect nicotine will reduce error rates in control blocks consistent with previous reports of improved attention with acute dosing of transdermal nicotine. We expect to find an interaction between valence and treatment such that performance improves with nicotine to a significantly greater extent in negative valence blocks. We further expect this increase to be more prominent in individuals with schizophrenia than in healthy controls. We expect salivary nicotine concentration, which is proportional to serum nicotine, will correlate with improvement in response inhibition. Based on previous findings in the Emotional Go/NoGo task, we do not expect to find an effect of antipsychotic exposure, as measured by chlorpromazine equivalents.

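### Treatment order is not stated to be stratified by diagnosis and the models have no period term, so a chance order imbalance could shift the realised nicotine effect in patients and its contrast with controls

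*Combined protocol and SAP*

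**What the plan says.** Section 5.4 is the whole account of allocation: "Treatment order will be block randomized", by someone who is otherwise outside the study, with investigators and subjects blinded to order. It gives no block size or stratification factor, and does not say whether patients and controls share a list.

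The design is a two-period crossover (section 6.2): "On day 2, subjects will receive the treatment they did not receive on day 1". The rest of the second session repeats the first. Section 6.1 allows screening to be combined with the first testing session for some subjects, and section 8.1.2 accepts that screening assessments or tasks may cause fatigue.

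Section 12.1 sizes the patient group at 25 completers from 30 enrolled and adds "We will match this group with a healthy control sample of similar size".

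The models in section 12.2 contain a random subject effect, treatment, block valence and their interaction. They have no term for period, sequence or diagnosis. The section nevertheless anticipates a group difference: "We further expect this increase to be more prominent in individuals with schizophrenia than in healthy controls".

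**The concern.** In a two-period crossover, a change in performance from day 1 to day 2 cancels from the treatment effect when half the subjects receive each order. If order is unbalanced within a group, part of the day effect is counted as a nicotine effect unless the model removes it.

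Blocking on a single list balances order over all subjects, not within each diagnostic group. With equal group sizes and overall balance, any excess of nicotine-first among patients is matched by the same deficit among controls. The two groups' nicotine effects then shift in opposite directions, and their difference carries both shifts.

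A day effect is plausible from the protocol. The same task is repeated, no practice session is described, and where visits are combined day 1 can carry the screening load that day 2 does not. At stake are the within-patient nicotine effect, on which the study is sized, and any patient-control comparison of it.

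**Working it through.** **Inputs.** From section 12.1: 25 completers, 30 patients enrolled, controls of similar size (taken as 30 enrolled and 25 completing), reaction-time effect 0.6, alpha 0.05, dropout about 15%. Assumed: two-sided test, blocks of 4 or 6, and a day effect P of 0 to 1, in SDs of the within-subject nicotine-minus-placebo difference. The documents give no value for P.

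**The plan's own figures.** A paired t-test with n = 25 and effect size 0.6 has noncentrality 0.6 × √25 = 3.0 and power 82.1%. The smallest n for 80% is 24. Enrolment is 25 / (1 − 0.15) = 29.4, so 30. The reaction-time sizing is reproduced. The documents give no figure for order balance.

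**Chance of imbalance, one list, mixed enrolment.** The number of nicotine-first subjects among 30 patients, with 30 nicotine-first orders among 60 subjects, is hypergeometric (60, 30, 30).
- P(17:13 or worse, either direction) = 0.44
- P(18:12 or worse, either direction) = 0.196

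Simulation with blocks of 4 and 6 agrees (0.44; 0.19 to 0.20). The groups' imbalances are in opposite directions in 79% of simulated trials; nearly all the rest are exact ties.

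**Shift at 18:12.** Write a subject's difference as D = τ − P·s, with s = +1 for nicotine first and −1 for placebo first.
- Patients: mean s = (18 − 12)/30 = 0.2, a shift of size 0.2P.
- Controls at 12:18: mean s = −0.2, a shift of 0.2P the other way.
- Patient-control difference: 0.2P + 0.2P = 0.4P.

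For P = 0.25, 0.5 and 1 SD, the patient effect moves by 0.05, 0.10 and 0.20 SD, and the group difference by 0.10, 0.20 and 0.40 SD.

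**Spread over all randomisations.** Let k be mean s in patients minus mean s in controls.

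| 30 + 30 subjects | SD of k | 95% of \|k\| within |
|---|---|---|
| One list, mixed enrolment | 0.26 | 0.53 |
| One list, all patients first, blocks of 4 | 0.08 | 0.13 |
| One list, all patients first, blocks of 6 | 0 | 0 |
| Separate lists, blocks of 4 | 0.05 | 0.13 |
| Separate lists, blocks of 6 | 0 | 0 |

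The mean of k is zero to within simulation error in every row. At P = 0.5 SD, the 95% range of the shift falls from 0.5 × 0.53 = 0.27 SD on one list to at most 0.5 × 0.13 = 0.07 SD on separate lists.

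**Precision with 25 + 25 completers.** SD of the group difference = √(2/25 + P² × SD(k)²).
- One list, SD(k) = 0.26 as at enrolment: 0.290, 0.311 and 0.384 for P = 0.25, 0.5 and 1.
- One list run at 25 + 25, where SD(k) is 0.287: 0.292, 0.317 and 0.403. Direct simulation gives 0.293, 0.315 and 0.404.
- Separate lists, simulated: 0.284, 0.286 and 0.291.

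**Type I error and the period term (simulated, 25 + 25).**

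| Allocation and model | P = 0 | P = 0.5 | P = 1 |
|---|---|---|---|
| One list, no period term | 4.9% | 4.7% | 5.2% |
| One list, period term | 5.0% | 4.7% | 5.2% |
| Separate lists, no period term | 4.8% | 3.1% | 0.8% |
| Separate lists, period term | 4.8% | 5.1% | 5.2% |

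With a period term on one list, the SD of the group difference stays at 0.284 to 0.288. Separate lists without a period term make the test conservative, because the day effect stays in the residual variance. The two changes belong together.

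**The case against.** **Separate lists are not ruled out.** This stands. Section 5.4 is silent; one shared list is an inference. If separate lists already exist, one sentence settles the allocation half of the point.

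**The 20% depends on mixed enrolment.** This also stands. The plan to match controls to patients is compatible with enrolling patients first, and the imbalance then almost vanishes. No enrolment sequence is stated.

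**It is not bias.** Correct. A reader might infer that the group comparison is systematically biased. It is not: the unadjusted group difference averages within 0.005 of zero, with type I error of 4.7% to 5.2%. The cost is a shift in the trial actually run and a loss of precision.

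**The anticipated comparison is of a different quantity.** The increase expected to be larger in patients reads most naturally as the extra nicotine benefit in negative-valence blocks, that is, diagnosis by treatment by valence. Each session contains both block types, so a day effect common to them cancels. The 0.4P therefore applies to a patient-control comparison of the nicotine effect itself, and to the valence interaction only if the day effect differs by valence. The within-patient nicotine effect remains exposed.

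**The shift cannot be scaled against 0.6.** A reader might set 0.2 SD against the 0.6 in section 12.1 and call it a third of the target. That 0.6 is a within-person difference between conditions. The plan states no power for any group contrast, so the ratio has no meaning.

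**A period term suffices.** Largely true when the day effect is the same in both groups. A common period term does not fully correct if practice or fatigue differs by diagnosis; order balanced within each group guards against that by design. Stratified lists in turn balance order only at enrolment, and about 15% dropout can disturb it.

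**Conclusion.** The point holds as a low-cost improvement to design and analysis. Neither the stated allocation nor the stated models protect the nicotine effect within patients, or its comparison with controls, from a day effect.

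The size depends on three things the documents do not give: one shared list, mixed enrolment, and a day effect P. Under the first two, about one trial in five has a patient split of 18:12 or worse. With P = 0.5 SD, the SD of the group difference rises from about 0.28 to about 0.31. In variance terms, (0.284/0.315)² = 0.81, a loss equivalent to about 19% of the sample. At P = 1 SD the SD is 0.38 to 0.40, depending on whether balance is taken at 30 or 25 per group. With no day effect, or with patients enrolled first, the loss is nil or close to it.

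The documents support neither a claim of systematic bias or inflated type I error, nor a claim that the treatment-by-valence interaction is compromised by a day effect common to both block types.

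**What to change.** In section 5.4, state: *Order of treatment will be randomised in permuted blocks, using separate lists for schizophrenia subjects and healthy controls.* Record the block size where blinded staff cannot see it.

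In section 12.2, add to both models a fixed effect for period (day 1 or day 2), and diagnosis with its interactions with treatment and valence, so that the anticipated group difference has a term that estimates it. Add diagnosis by period if the day effect may differ between groups. The period term also deals with imbalance brought back by dropout.

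The cost is one sentence and two lists instead of one, a few degrees of freedom, and no extra subjects or visits. If enrolment has begun, the lists can change only for later subjects; the model terms can still be specified before unblinding.
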